4.1. RANDOMIZATION

No specific methods for assigning subjects will be used for this clinical investigation. A consecutive series of subjects at each site meeting all the eligibility criteria will be enrolled in this clinical investigation.

4.2. STATISTICAL INTERIM ANALYSES AND STOPPING GUIDANCE

Interim analyses will be performed on a yearly basis. The progress of the clinical investigation will be reported together with the interim results on the variable level according to the analysis plan.

The analysis of the primary endpoint / objective will be part of the related interim / annual report when all subjects have completed the 24 months post-operative including the ASES score.

There will be no stopping rules specified for this clinical investigation.

4.3. TIMING OF FINAL ANALYSES

The full final report with complete analyses, progress and conduct reporting will be created at the end of this clinical investigation.

4.4. TIMING OF OUTCOME ASSESSMENT

Subjects in this clinical investigation will be evaluated at Pre-Operative, Operative/Discharge, and at 6 Weeks (4 weeks – 8 weeks), 6 Months (24 weeks – 28 weeks), 12 Months (48 weeks- 56 weeks), 24 Months (100 weeks – 108 weeks) and annually (up to ten years) after the index procedure. The follow up evaluations will include assessment of complications and adverse events and ASES Shoulder Score.

Assessment	Pre-Operative	Operative/ Discharge	6 Weeks ^{a, b} (+/- 2 weeks)	6 Months ^{a, b} (+/- 3 weeks)	12 Months ^{a, b} (+/- 4 weeks)	24 Months ^{a, b} (+/- 4 weeks)	Annually ^b (+/- 4 weeks)
Informed Consent	X						
Demographics & Medical History	X						
Inclusion/Exclusion	X						
Primary Diagnosis	X						
Surgical Procedure		X					
ASES Shoulder Score	X		X	X	X ^c	X ^c	X ^c
Subject Disposition ^d			X	X	X	X	X
	Device-Related AEs/Incidents & Reoperations will be collected throughout the course of the clinical investigation.						
	a. Follow-up visit schedule to reflect Institutions’ Standard of Care practices b. If the subject missed a visit and outside of visit window, every effort should be made to collect data instead of noting visit as missed. Visit windows are calculated from index event, and not from previous visit. c. Evaluation can be collected via phone. d. Subject Disposition assessment would occur at any time point for subject withdrawal prior to the completion of the clinical investigation.						

Table 4.4: Schedule of Events

4.5. STATISTICAL SOFTWARE

Statistical Analysis will be performed using IBM SPSS, IBM SPSS Sample Power as well as established standard software packages (e.g. MS Excel).

4.6. MISSING DATA

The intent is to collect as complete a dataset as possible. Nevertheless, in some situations missing data cannot be avoided. The reports and tables therefore will show the number and percentage of missing cases for each analyzed variable in relation to the enrolled cases for each post-operative assessment

Any deviations from Statistical Analysis Plan will be listed in the annual or final reports.

4.7. CONFIDENCE INTERVALS AND P-VALUES

The following acceptance / rejection criteria were used for this clinical investigation:

Parameter	Acceptance / rejection criteria
Confidence level (1- α)	0.95 (95%)
Significance level (α)	0.05 (5%)
Power (1- β)	0.80 (80%)
Beta-level (β)	0.20 (20%)
Confidence interval of mean	95%
p-value indicating significance	≤ 0.05

Table 4.7: Acceptance / Rejection Criteria

4.8. UNITS

See analysis chapter for details related to units used for the different variables and calculations.

In case of collection of variables with non-SI units (e.g. pounds instead to kilograms), conversion of such data into SI units (and vice versa) will be ensured and both results will be reported for the full set of available subjects next to each other in the interim/annual and/or final reports.

4.9. CALCULATIONS AND TRANSFORMATIONS

Distances between times and differences between score results will be calculated. For full details of variables used for calculations and the creation of new variables based on these calculations, see analysis chapter.

4.10. ASSUMPTIONS

In case of deviation from assumptions (e.g. normality), non-parametric methods will be used for analysis. No transformation of such data will be performed.

5. Population and Progress

5.1. ANALYSIS POPULATION

It is expected, that during this clinical investigation only one population for ReUnion RFX System will exist and all subjects will be analyzed “Per Protocol” (PP). However, it cannot be fully avoided that in theory subjects might need to be excluded from the PP population. In this occasion, there will be two groups being fully analyzed to ensure transparency and avoid bias.

The groups are defined as follows:

- **Intent-to Treat Population**

The Intent-to-Treat (ITT) Population is defined to be all enrolled subjects. An enrolled subject is a subject that has signed informed consent, all screening procedures have been successfully completed, is eligible and can receive treatment. The ITT population will not be analyzed for the annual reports and will only be included in the final report.

- **Per Protocol Population**

The Per Protocol (PP) Population is defined to be all subjects in the ITT Population with no major clinical investigation plan / protocol violations. The clinical investigation plan / protocol violations that will exclude a subject are as follows:

- The subject does not receive the ReUnion RFX System
- The subject does not meet all eligibility criteria
- The subject has a clinical investigation plan / protocol violation that is considered likely to affect subject outcomes.

After the clinical investigation has been completed, a review of the data will be conducted to determine which subjects are to be excluded from the PP population.

The following tables will be created for interim/annual and final reports related to the clinical investigation populations and progress:

Evaluation Variable / Question	Level of Measurement	Analysis Plan
All Forms – Overview & Progress Report		
Counting of available subjects Subject Population by Site (Variable(s): SITENUM; SUBID)	Qualitative, nominal	Proportions, frequencies, column and row totals, missing proportion (if any).
Counting of available subjects Subject Population by Visit (Variable(s): SITENUM; SUBID; VISITDT)	Qualitative, nominal	Proportions, frequencies, column and row totals, missing proportion (if any).
Counting of available subjects Subject Population by Visit and by Site (Variable(s): SITENUM; SUBID; VISITDT)	Qualitative, nominal	Proportions, frequencies, column and row totals, missing proportion (if any).

Table 5.1: Populations and Progress Tables List

5.2. ELIGIBILITY

A subject is defined as eligible if all inclusion and exclusion criteria are fulfilled as it is described in the protocol. For details see CIP.

For tables to be created for the interim/annual and final reports, see chapter 6.2 and tables list 6.2.2.

5.3. WITHDRAWAL / FOLLOW-UP

If, during the clinical investigation, a subject must be prematurely withdrawn from clinical investigation, procedures are outlined in the CIP. These procedures should not interfere with the initiation of any new treatments that are necessary to treat a subject’s condition. Information on all withdrawn subjects will be documented.

The following tables will be created for interim/annual and final reports related to the numbers of withdrawn subjects (if any) divided into both groups (Arm A; Arm B):

Evaluation Variable / Question	Level of Measurement	Analysis Plan
All Forms – Overview & Progress Report		
Counting of withdrawn subjects Number of Subjects Withdrawn by Site (Variable(s): SITENUM; COMPPROT; PRIMRSN)	Qualitative, nominal	Proportions, frequencies, column and row totals, missing proportion (if any).
Counting of withdrawn subjects Number of Subjects Withdrawn by Site by Visit (Variable(s): SITENUM; COMPPROT; PRIMRSN; VISITDT)	Qualitative, nominal	Proportions, frequencies, column and row totals, missing proportion (if any).
Comments related to Reasons for Subjects Withdrawn (Variable(s): RSNSPF)	Text, String	Listing of reasons for subjects being excluded by subject code/ID

Table 5.3: Withdrawal Tables List

5.4. ADHERENCE AND CIP DEVIATIONS

Any CIP deviations will be listed in the interim/annual and final reports. It is optional to describe this chapter in free text or present it in a tabulated format.

6. Analysis

The following tabulated analysis plan reflects this approach and specifies the variables characteristics (quantitative or qualitative) in detail together with the related analysis strategy. This also includes calculation and summaries based on primary elements and the required analysis.

All analyses described in this section, will be split in the two groups (Arm A; Arm B).

In addition, it will be defined in the text or directly in the tables below, if the variable must be included in an interim/annual report (IR) and/or in the final report (FR).

6.1. HARMS AND SAFETY

Categorization and definitions of (Serious-, Unanticipated-) Adverse Device Effects, (Serious-) Incidents are given in the CIP.

Evaluation Variable / Question	Level of Measurement	Analysis Plan	Inclusion		
Adverse Events / Incidents			IR	FR	N/A
Perioperative/Postoperative AE (Variable(s): PERPOST)	Qualitative, nominal	Proportions, frequencies, column and row totals, missing proportion (if any).	X	X	
Device-Related Adverse Event / Incident (Variable(s): AEEVENT; AEOTHER)	Qualitative, nominal	Proportions, frequencies, column and row totals, missing proportion (if any). Listing of other Events/Incidents.	X	X	
Describe the AE/Incident (Variable(s): AEDESCRP)	Qualitative, nominal	Listing of other Events/Incidents Description.			X
Unanticipated Adverse Device Event? (Variable(s): AEUADE)	Qualitative, nominal	Proportions, frequencies, column and row totals, missing proportion (if any).	X	X	
Severity (Variable(s): AESEVER)	Qualitative, nominal	Proportions, frequencies, column and row totals, missing proportion (if any).	X	X	
Action Taken (Variable(s): ACTNONE; ACTMEDS; ACTSURG; ACTSHORT;	Qualitative, nominal	Proportions, frequencies, column and row totals, missing proportion (if any).			X

ACTPROHS; ACTOTHER; ACTOTHSP)		Listing of given Other specifications.			
AE Resolution (Variable(s): AERESOLV)	Qualitative, nominal	Proportions, frequencies, column and row totals, missing proportion (if any).			X
Outcome (Variable(s): AEONWOTR; AEONWTTR; AEREWOTR; AEREWTTR; AETEDISB; AEPERMD; AESUEXP)	Qualitative, nominal	Proportions, frequencies, column and row totals, missing proportion (if any).			X
Creation of variable Number of Adverse Device Effects by Site (Variable(s): AEEVENT; SITENUM)	Qualitative, nominal	Proportions, frequencies, column and row totals, missing proportion (if any).	X	X	
Creation of variable Number of Adverse Device Effects per Subject and Site (Variable(s): AEEVENT; SITENUM; SUBID)	Qualitative, nominal	Proportions, frequencies, column and row totals, missing proportion (if any).	X	X	

Table 6.1.1: Adverse Events / Incidents Tables List

Evaluation Variable / Question	Level of Measurement	Analysis Plan	Inclusion		
			IR	FR	N/A
Reoperation					
Type of Procedure (Variable(s): IRRDEB; SOFTTRL; ROTCFRP; OTHTISRP; RVHARSA; RVHARSASP; REVRSA; REVRASASP; CHATSAWHS; CHATSAWOHS; CHARSAWHS; CHARSAWOHS; CTSAAWHS; CTSAAWOHS; CTSARSAWHS; CTSARSAWOHS; CRSAWHS; CRSAWOHS; REVFINF; REVFINFSP; RESARTH; ARTHOD; ORIF; RESOSSIF; TYPEOTH; TYPEOTHSP)	Qualitative, nominal	Proportions, frequencies, column and row totals, missing proportion (if any). Listings of implant specifications.	X	X	
Reason(s) for Reoperation (Variable(s): WOUNCOM; INFEC; NERPAL; DISLC; OTSUBLUX; MALPOS; UNDROVR; IMPDISL; ROTCFTR; ERGLEN; IMPLOOS; IMPBRKG; WRGLEN; PERFRAC; STIFF; PAIN; HETOSSIF; RESOTH; RESOTHSPC)	Qualitative, nominal	Proportions, frequencies, column and row totals, missing proportion (if any). Listings of other specifications.	X	X	

Table 6.1.2: Reoperation Tables List

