### 13.2. ADVERSE EVENT SEVERITY

The severity of all AEs is assessed by the Investigator utilizing the following categories:

- **Mild:** The AE is transient and easily tolerated by the subject.
- **Moderate:** The AE causes the subject discomfort and interrupts the subject's usual activities.
- **Severe:** The AE causes considerable interference with the subject's usual activities and may be incapacitating or life-threatening, including those events resulting in a subject's disability or permanent damage, and/or required intervention to prevent permanent disability or damage.
- **Life-Threatening:** The AE results in a life-threatening illness or injury.
- **Fatal:** The AE results in death.

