### 13.4. ADVERSE EVENT/INCIDENT REPORTING

In the event a SADE, UADE or serious incident occurs, the Investigator is required to notify the Sponsor within 48 hours of being made aware of the event. The Investigator also is required to notify their IRB in accordance with the policies of their local laws and regulations.

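### SAP Table 6.1.1 plans no count of serious device effects or serious incidents, and it leaves the collected Action Taken and Outcome items out of both reports

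*SAP*

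**What the plan says.** CIP 13.1 defines five categories: adverse device effect, incident, SADE, serious incident and UADE. CIP 13.4 attaches a deadline to three of them: "In the event a SADE, UADE or serious incident occurs, the Investigator is required to notify the Sponsor within 48 hours".

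SAP 6.1 opens by adopting these categories: "Categorization and definitions of (Serious-, Unanticipated-) Adverse Device Effects, (Serious-) Incidents are given in the CIP". The introduction to SAP section 6 explains the inclusion columns, which show "if the variable must be included in an interim/annual report (IR) and/or in the final report (FR"). The remaining column is N/A.

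Table 6.1.1 then lists the adverse event items. Three of the rows marked N/A are:

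- "Action Taken (Variable(s): ACTNONE; ACTMEDS; ACTSURG; ACTSHORT" and three further action variables
- "AE Resolution (Variable(s): AERESOLV")
- Outcome ("Variable(s): AEONWOTR; AEONWTTR; AEREWOTR; AEREWTTR; AETEDISB; AEPERMD; AESUEXP")

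The free-text description of the event is also N/A. Severity and the UADE flag are marked for both reports. CIP section 11 states that the SAP covers every variable and question in the investigation, so the serious categories cannot be assumed to sit in some other list.

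**The concern.** Safety is half of the stated objective, and CIP section 13 places the study within post-market reporting under the European device regulation, using the incident categories. The events that the protocol treats as most urgent are the only ones in 13.1 for which the SAP plans no count. The items a reader might use to judge consequences are collected and then left out of the reports.

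Follow-up runs to 10 years with a report each year. Without a planned count, the number of serious device effects and serious incidents per arm is not a required output of any of those reports. If it does appear, the SAP fixes neither the rule used to classify events nor the unit counted (events or subjects).

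**Working it through.** No formula applies. The check reads Table 6.1.1 row by row and compares what is tabulated with the definitions in CIP 13.1.

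**Step 1. Row count of Table 6.1.1**

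- Marked for annual and final report (6 rows): perioperative or postoperative timing, event type, UADE flag, severity, number of device effects by site, number of device effects per subject and site.
- Marked N/A (4 rows): description, action taken, resolution, outcome.
- Total 6 + 4 = 10 rows. Rows for SADE, SAE or serious incident status: 0.
- Variables in the Action Taken and Outcome rows: 7 + 7 = 14.

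**Step 2. What makes an event serious under CIP 13.1**

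- A SADE may qualify in several ways. Its consequences may be those of an SAE. It may be capable of such consequences if nothing is done. It may interfere considerably with usual activities, in words close to the Severe grade in 13.2. Or it may be life-threatening or fatal.
- A serious incident is any incident that led to, could have led to, or could lead to death, serious deterioration in health or a serious public health threat. An incident includes a device malfunction, so no actual harm is needed.
- 13.1 does not define SAE, although the SADE and UADE definitions both depend on it.

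**Step 3. What the planned tables capture**

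| Planned output | Reports | What it covers | What it misses |
|---|---|---|---|
| Severity (Table 6.1.1; grades in CIP 13.2) | Annual and final | Severe, Life-Threatening and Fatal grades, close to the interference, life-threatening and fatal limbs of the SADE definition | SADEs graded Mild or Moderate that qualify through SAE-type or potential consequences; serious incidents that could have caused harm |
| UADE flag (Table 6.1.1) | Annual and final | Serious or potentially serious effects not described in the consent, CIP or labeling | Serious events of the types listed in CIP 13.5, such as deep infection, pulmonary embolism, severe nerve injury and periprosthetic fracture |
| Reoperation type and reason (Table 6.1.2) | Annual and final | Events treated by reoperation | Serious events managed without reoperation; no planned link to serious status |
| Time to first reoperation (SAP 6.7.3) | Final | Timing of the first reoperation | As above |
| Mortality (SAP 6.7.2) | Final | Deaths | Non-fatal serious events |

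The UADE entry follows from the definition. An event type that the CIP itself lists as foreseeable is described in the CIP, so it is not unanticipated. The flag therefore excludes the serious harms one would most expect in shoulder arthroplasty.

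**Step 4. Whether serious status could be derived from the N/A items**

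Only in part. The documents give no dictionary for the action and outcome codes, so their meanings can only be guessed from the abbreviations. Even with a dictionary, codes for what was done and how the event ended cannot identify an event that merely could have caused serious harm. They also cannot settle which consequences belong to an SAE when that term is undefined. A direct classification by the investigator is needed.

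**The case against.** The strongest reply is that the reports are far from silent on serious harm. Severity is graded by the investigator, and its upper grades are defined by consequence. The Severe grade covers events that "may be incapacitating or life-threatening, including those events resulting in a subject's disability or permanent damage", and Life-Threatening and Fatal follow. SAP 7.1 requires every answered option to be shown with its count. UADEs are counted in both reports. Reoperations are tabulated in both, and mortality and time to reoperation are in the final report. Each SADE and serious incident reaches the sponsor by notification. The safety endpoint in CIP 8.3 is the incidence of device-related events, with no separate endpoint for serious ones.

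Most of this stands, and it rules out three stronger readings that a reader might infer:

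- That no report could ever give the number of serious events. The inclusion columns set the required content and do not forbid more, and the sponsor holds the notifications. The documents support only that no count is planned.
- That surgery and deaths would go unseen. Reoperations and the Fatal grade appear in both reports, and mortality in the final report. Permanent damage falls within the Severe grade, although it is not shown separately.
- That most of the items bearing on seriousness are withheld. Severity, UADE and the reoperation rows all bear on it and are all reported.

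The mention of life-threatening events in both the Severe and the Life-Threatening grades is a minor wording matter. It disappears when the upper grades are added together, and the point does not rest on it.

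The reply does not supply the missing count. Severe, Life-Threatening and Fatal events added together are not the 13.1 categories, and nothing in the SAP carries the notifications into a report.

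**Conclusion.** The point holds as a gap in the planned safety tables: no row counts SADEs or serious incidents, and the 14 Action Taken and Outcome variables are collected but left out of both reports. The severity, UADE, reoperation and mortality tables form a substantial but incomplete proxy. How many serious events the proxy would miss cannot be estimated, because the documents give no expected event rates.

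The conclusion rests on three assumptions: that the inclusion marks in Table 6.1.1 belong to the columns they stand in, that the SAP's variable list is complete as CIP section 11 says, and that an event type listed in CIP 13.5 counts as described for the UADE definition. It does not rest on the meaning of any variable code.

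The primary endpoint is not affected. This is a cheap improvement to what the study can say on its safety objective.

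**What to change.** - Add two rows to Table 6.1.1, SADE (yes/no) and serious incident (yes/no). The investigator classifies each event by CIP 13.1, and the result is reconciled with the 48-hour notifications. Mark both rows for the annual and the final report, by arm, with counts of events and of subjects.
- Move Action Taken and Outcome from N/A to both reports.
- Define SAE in CIP 13.1, since SADE and UADE depend on it.

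The cost is one or two added items on the adverse event form, a short clarification of the CIP and a little more table work each year. Investigators already have to recognise these events in order to notify them, so the added burden is small. Events recorded before the change would need classifying once, with the notifications as the starting point.

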6.2. BASELINE CHARACTERISTICS

Evaluation Variable / Question	Level of Measurement	Analysis Plan	Inclusion		
			IR	FR	N/A
Preoperative Visit Form – Subject Eligibility – Inclusion & Exclusion Criteria					
Note: Inclusion and exclusion criteria will be checked during monitoring and reported by a statement (e.g. all subjects fulfilled the inclusion criteria).					
Inclusion Criteria Questions (Variable(s): INCLA; INCLB; INCLC; INCLD)	Qualitative, nominal	Proportions, frequencies, column and row totals, missing proportion (if any).			X
Exclusion Criteria Questions (Variable(s): EXCLA; EXCLB; EXCLC; EXCLD; EXCLE; EXCLF; EXCLG)	Qualitative, nominal	Proportions, frequencies, column and row totals, missing proportion (if any).			X

Creation of variable No. of Eligible Subjects. Conclusion of Inclusion and Exclusion Questions.	Qualitative, nominal	Proportions, frequencies, column and row totals, missing proportion (if any).			X
--	----------------------	---	--	--	---

Table 6.2.1: Preoperative Visit Form - Subject Eligibility – Inclusion & Exclusion Criteria Tables List

Evaluation Variable / Question	Level of Measurement	Analysis Plan	Inclusion		
			IR	FR	N/A
Preoperative Visit Form - Subject Demographics					
Creation of variable Age [years] Difference between Date of Surgery [dd.mmm.yyyy] and Date of Birth/DOB [dd.mmm.yyyy] in [] years [] (Variable(s): BIRTHDT; VISITDT; VISNAME)	Quantitative, ratio	Case summary with number and percentage of valid cases/values, missing cases/values (if any) and total cases/values. Mean, median, interquartile range, maximum, minimum, standard deviation, 95% confidence interval for mean, Shapiro-Wilk Test.	X	X	
Gender (Variable(s): GENDER)	Qualitative, nominal	Proportions, frequencies, column and row totals, missing proportion (if any).	X	X	
Race (Variable(s): AMERIND; ASIAN; BLKAFR; NATHAW; CAUS; RACEOTH; RACEOTHR)	Qualitative, nominal	Proportions, frequencies, column and row totals, missing proportion (if any). Listing of given specifications.	X	X	
Height [captured in inches] In the analysis, all values will be reported in inches and cm next to each other. (Variable(s): HGHTM)	Quantitative, ratio	Case summary with number and percentage of valid cases/values, missing cases/values (if any) and total cases/values. Mean, median, interquartile range, maximum, minimum, standard deviation, 95% confidence interval for mean, Shapiro-Wilk Test.			X
Weight [captured in lbs] In the analysis, all values will be reported in lbs and kg next to each other. (Variable(s): WEIGHTKG)	Quantitative, ratio	Case summary with number and percentage of valid cases/values, missing cases/values (if any) and total cases/values. Mean, median, interquartile range, maximum, minimum, standard deviation, 95% confidence interval for mean, Shapiro-Wilk Test.			X
Body Mass Index [kg/m²] (Variable(s): BMI)	Quantitative, ratio	Case summary with number and percentage of valid cases/values, missing cases/values (if any) and total cases/values. Mean, median, interquartile range, maximum, minimum, standard deviation, 95% confidence interval for mean, Shapiro-Wilk Test.	X	X	

Table 6.2.2: Preoperative Visit Form - Subject Demographics Tables List

Evaluation Variable / Question	Level of Measurement	Analysis Plan	Inclusion		
			IR	FR	N/A
Preoperative Visit Form – Current Relevant Medical Conditions					
Current Relevant Medical Conditions (Variable(s): CURCOND; CONDSPC)	Qualitative, nominal	Proportions, frequencies, column and row totals, missing proportion (if any).	X	X	

		Listing of given specifications.			
--	--	----------------------------------	--	--	--

Table 6.2.3: Preoperative Visit Form - Current Relevant Medical Conditions

Evaluation Variable / Question	Level of Measurement	Analysis Plan	Inclusion		
			IR	FR	N/A
Preoperative Visit Form – Subject Evaluation					
Tobacco Use: (Variable(s): TOBCCO)	Qualitative, nominal	Proportions, frequencies, column and row totals, missing proportion (if any).	X	X	
Corticosteroids Taking: (Variable(s): CORTICO)	Qualitative, nominal	Proportions, frequencies, column and row totals, missing proportion (if any).	X	X	
Affected (Study) Shoulder (Variable(s): AFFCSHL)	Qualitative, nominal	Proportions, frequencies, column and row totals, missing proportion (if any).	X	X	
Primary Shoulder Diagnosis: (Variable(s): PRIMDIAG)	Qualitative, nominal	Proportions, frequencies, column and row totals, missing proportion (if any).	X	X	
Shoulder Arthroplasty Procedure: (Variable(s): SHLARPROC)	Qualitative, nominal	Proportions, frequencies, column and row totals, missing proportion (if any). Listing of given specifications.	X	X	
Previous History of Surgery to the Affected Shoulder (Variable(s): PREVHIST)	Qualitative, nominal	Proportions, frequencies, column and row totals, missing proportion (if any). Listing of given specifications.		X	
Procedure 1 (Variable(s): PROCNM1)	Text, String	Listing of comments and dates together identified by subject code/ID			X
Procedure Date 1 (Variable(s): PROCDT1)	Quantitative, ratio Date/Time				X
Procedure 2 (Variable(s): PROCNM2)	Text, String	Listing of comments and dates together identified by subject code/ID			X
Procedure Date 2 (Variable(s): PROCDT2)	Quantitative, ratio Date/Time				X
Procedure 3 (Variable(s): PROCNM3)	Text, String	Listing of comments and dates together identified by subject code/ID			X
Procedure Date 3 (Variable(s): PROCDT3)	Quantitative, ratio Date/Time				X
Procedure 4 (Variable(s): PROCNM4)	Text, String	Listing of comments and dates together identified by subject code/ID			X
Procedure Date 4 (Variable(s): PROCDT4)	Quantitative, ratio Date/Time				X

Table 6.2.4: Preoperative Visit Form – Medical History Tables List

Evaluation Variable / Question	Level of Measurement	Analysis Plan	Inclusion		
			IR	FR	N/A
Preoperative Visit Form – ASES Shoulder Score (prior to surgery)					
Q1 - Usual Work (Variable(s): USWORK)	Text, String	Listing of comments identified by subject code/ID			X
Q2 - Usual Sport/Leisure activity? (Variable(s): USSPRT)	Text, String	Listing of comments identified by subject code/ID			X
Q3 - Do you have shoulder pain at night? (Variable(s): PNNIGHT)	Qualitative, nominal	Proportions, frequencies, column and row totals, missing proportion (if any).			X
Q4 - Do you take pain killers such as paracetamol (acetaminophen), diclofenac, or ibuprofen?	Qualitative, nominal	Proportions, frequencies, column and row totals, missing proportion (if any).			X

(Variable(s): PNKLR)					
Q5 - Do you take strong pain killers such as codeine, tramadol, or morphine? (Variable(s): CODTRMD)	Qualitative, nominal	Proportions, frequencies, column and row totals, missing proportion (if any).			X
Q6 - How many pills do you take on an average day? (Variable(s): PILLNUM)	Quantitative, ratio	Case summary with number and percentage of valid cases/values, missing cases/values (if any) and total cases/values. Mean, median, interquartile range, maximum, minimum, standard deviation, 95% confidence interval for mean, Shapiro-Wilk Test.			X
Q7 - Intensity of pain? (Variable(s): PAINC)	Quantitative, ratio	Case summary with number and percentage of valid cases/values, missing cases/values (if any) and total cases/values. Mean, median, interquartile range, maximum, minimum, standard deviation, 95% confidence interval for mean, Shapiro-Wilk Test.			X
Q8 - Is it difficult for you to put on a coat? (Variable(s): PUTCOAT)	Qualitative, ordinal	Proportions, frequencies, column and row totals, missing proportion (if any).			X
Q9 - Is it difficult for you to sleep on the affected side? (Variable(s): DIFSLP)	Qualitative, ordinal	Proportions, frequencies, column and row totals, missing proportion (if any).			X
Q10 - Is it difficult for you to wash your back/do up bra? (Variable(s): WASHBCK)	Qualitative, ordinal	Proportions, frequencies, column and row totals, missing proportion (if any).			X
Q11 - Is it difficult for you manage toileting? (Variable(s): MNGTOIL)	Qualitative, ordinal	Proportions, frequencies, column and row totals, missing proportion (if any).			X
Q12 - Is it difficult for you to comb your hair? (Variable(s): COMBHR)	Qualitative, ordinal	Proportions, frequencies, column and row totals, missing proportion (if any).			X
Q13 - Is it difficult for you to reach a high shelf? (Variable(s): HIGHSHL)	Qualitative, ordinal	Proportions, frequencies, column and row totals, missing proportion (if any).			X
Q14 - Is it difficult for you to lift 10lbs. (4.5kg) above your shoulder? (Variable(s): LIFT10)	Qualitative, ordinal	Proportions, frequencies, column and row totals, missing proportion (if any).			X
Q15 - Is it difficult for you to throw a ball overhand? (Variable(s): BALLOV)	Qualitative, ordinal	Proportions, frequencies, column and row totals, missing proportion (if any).			X
Q16 - Is it difficult for you to do your usual work? (Variable(s): DFWORK)	Qualitative, ordinal	Proportions, frequencies, column and row totals, missing proportion (if any).			X
Q17 - Is it difficult for you to do your usual sport/leisure activity? (Variable(s): SPRACT)	Qualitative, ordinal	Proportions, frequencies, column and row totals, missing proportion (if any).			X
ASES Pain Score [points] (Variable(s): PAINSC)	Quantitative, ratio	Case summary with number and percentage of valid cases/values, missing cases/values (if any) and total cases/values. Mean, median, interquartile range, maximum, minimum, standard deviation, 95% confidence interval for mean, Shapiro-Wilk Test.	X	X	
ASES Functioning Score [points] (Variable(s): FUNSCORE)	Quantitative, ratio	Case summary with number and percentage of valid cases/values, missing	X	X	

		cases/values (if any) and total cases/values. Mean, median, interquartile range, maximum, minimum, standard deviation, 95% confidence interval for mean, Shapiro-Wilk Test.			
Total ASES Shoulder Score [points] (Variable(s): FINSORE)	Quantitative, ratio	Case summary with number and percentage of valid cases/values, missing cases/values (if any) and total cases/values. Mean, median, interquartile range, maximum, minimum, standard deviation, 95% confidence interval for mean, Shapiro-Wilk Test.	X	X	

Table 6.2.5: Preoperative Visit Form – ASES Score (post fracture, prior to surgery) Tables List

